2.4.2.2. Safety Monitoring

Following our current IRB-35064, during and after the panitumumab-IRDye800 infusion, subjects will be monitored for allergic reactions. Safety measurements will be taken, including, as hemodynamic monitoring, ECGs, blood tests, and physical examination - see Section 9 for a specific list of measurements taken at the different timepoints (ie, screening, day of surgery).

If three or more participants of the study experience dose limiting toxicity (DLT), then the study will be stopped and the data reviewed. Dose-limiting toxicity (DLT) will be defined as any Grade 2 or greater toxicity that is considered possible, probably or definitely related to the study drug and considered clinically significant by the investigator, and occurs within 15 days of receiving treatment, which represents more than 4 half-lives of the drug. Restarting the study will require reassessment after discussion and approval by the Data Safety Monitoring Committee. Because panitumumab is an approved agent with a known DLT rate of 1%, we expect this study to further confirm the safety of conjugated panitumumab-IRDye800 at lower doses than the dose used in a therapeutic setting.

The known rate of severe infusion reactions of panitumumab is 1% (package insert, June 2017); therefore, we expect a DLT rate of approximately 1% or higher with panitumumab-IRDye800. Assuming the true DLT rate is as high as 5% and a significance level of 0.05, the probability of stopping early (three or more DLT in the first 12 subjects) is 0.002.

For Lymphoseek, no infusion reactions have been reported (see package insert) (28–30,32–34). The most common adverse reactions (incidence < 1%) are injection site irritation and pain (see Section 5.2.2.). Therefore, there is no implementation of additional safety measures warranted for this study.

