2.4.1. Number of subjects

A total of 20 subjects will be enrolled in our exploratory study.

Rationale for including cN0 and cN+ subjects: Based on NCCN guidelines, version 1 2018, SNB is justified in subjects with a T1 or T2 stage primary tumor and a cN0 neck that are at (high) risk for having LN metastasis. The strength of SNB lies in the identification of “skip lesions” (ie, metastatic spread to a LN outside the expected drainage area) and aberrant drainage patterns (ie, drainage to LNs that are outside the expected drainage template) (12-14). Including cN0 subjects will thus provide us with the unique opportunity to directly compare the performance of panitumumab-IRDye800 for metastatic LN identification to that of Lymphoseek and thus validate our approach against the reference standard.

Panitumumab-IRDye800 will be evaluated in subjects with any T stage and a cN+ neck to study how well panitumumab-IRDye800 can detect metastatic lesions in the LN(s).

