4.2 Administration of panitumumab-IRDye800

Administration of panitumumab-IRDye800 will be performed consistent with institutional policy for administration of panitumumab. The solution will be diluted to a total volume of 100mL using 0.9% sodium chloride injection, USP. Dosage level will be 50 mg panitumumab-IRDye800 (< 1/12 of a therapeutic dose of panitumumab). Administration of panitumumab-IRDye800 will occur by IV over 15 (\pm 5) minutes. Subjects will be observed for 30 (\pm 10) minutes after administration. Additional treatment for infusion reactions and electrolyte imbalances may be given following institutional policy.

Premedication will be delivered prior to the infusion for each subject at the discretion of the treating physician according to routine institutional protocols for delivery of panitumumab.

Treatment will be given in an infusion facility that routinely administers experimental chemotherapeutic infusions and is equipped with emergency equipment and medication along with medical personnel in the event that the subject experiences a severe reaction.

The infusion(s) will be stopped if deemed necessary with the onset of any significant signs of reaction. Steroids and other supportive medications may be administered and infusion resumed at the discretion of the treating physician. If a subject experiences a serious reaction that prevents completing the study infusion(s), the subject will be observed; but will not complete their study infusion(s). Any subject who does not receive the full panitumumab-IRDye800 dose will be considered withdrawn from the study and not count towards cohort accrual.

With a single dose at the levels proposed the half-life is expected to be approximately 2.3 days or less. Clearance of panitumumab occurs through the binding in the liver and through the reticuloendothelial system as occurs with endogenous immunoglobulin.

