4.4 Definition of Dose-Limiting Toxicity (DLT)

AEs will be graded according to the CTCAE v5.0 (<http://evs.nci.nih.gov/ftp1/CTAE/about.html>).

Dose-limiting toxicity (DLT) will be defined as any Grade 2 or greater toxicity that is ALL of the following:

- Determined by the investigator to be possible, probably or definitely-related to panitumumab-IRDye800 or Lymphoseek
- Considered by the Investigator to be clinically significant for subjects who received panitumumab-IRDye800 or Lymphoseek. For this study, clinically significant is defined based on NCI definition – a result that is large enough to affect a subject's disease state in a manner that is noticeable to the subject and/or caregiver or requires intervention
- Occurred within 15 days of receiving treatment with panitumumab-IRDye800 or Lymphoseek

The Stanford Data Safety Monitoring Committee (DSMC) will be notified of all DLTs. The DSMC will evaluate safety data from all subjects through Day of discharge. If 3 or more subjects experience a DLT, then study enrollment will be halted pending DSMC review.

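### The stated 0.002 chance of a safety stop at a 5% DLT rate should be 0.0196 for 12 subjects, and the rule as written runs over all 20, where it is 0.075

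*Combined protocol and SAP*

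**What the plan says.** Section 2.4.2.2 (Safety Monitoring) sets the rule: "If three or more participants of the study experience dose limiting toxicity (DLT), then the study will be stopped and the data reviewed". Section 4.4 (Definition of Dose-Limiting Toxicity) repeats it: "If 3 or more subjects experience a DLT, then study enrollment will be halted pending DSMC review". Neither version limits the count to a first group of subjects. On enrolment, Section 2.4.1 says: "A total of 20 subjects will be enrolled in our exploratory study". Table 1 divides these into two cohorts of 10.

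Section 2.4.2.2 starts from the known rate of severe infusion reactions to panitumumab and says "we expect a DLT rate of approximately 1% or higher with panitumumab-IRDye800". It then gives one operating characteristic for the rule. The premise is "Assuming the true DLT rate is as high as 5% and a significance level of 0.05" and the result is that "the probability of stopping early (three or more DLT in the first 12 subjects) is 0.002".

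Section 12 contains no safety calculation, so this sentence is the whole of the quantitative support for the rule.

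**The concern.** The sentence supplies everything needed to check it: a rate, a number of subjects and an event. Three or more events in 12 at 5% each is unlikely, but 1 in 500 looks too rare when the expected count is 12 × 0.05 = 0.6.

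Three further features do not fit the rule:

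- The calculation stops at 12 subjects. The rule does not, and no section defines a stage or look at 12.
- A significance level is quoted although no test is performed. Once the rate and the threshold of three are fixed, the probability of stopping is fixed too.
- The only rate considered is 5%, so the plan does not show how often the rule would trigger if the true rate were high.

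What is at stake is how a triggered rule is read. Restarting needs reassessment and approval by the Data Safety Monitoring Committee (DSMC). Anyone who took 0.002 at face value would see three DLTs as near-conclusive evidence that the rate exceeds 5%. With the correct figures the evidence is much weaker, particularly when the third DLT comes late in the study.

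**Working it through.** **Inputs.** True DLT rate p = 0.05, n = 12 and the event of three or more DLTs (all Section 2.4.2.2); total enrolment 20 (Section 2.4.1); expected rate about 1% (Section 2.4.2.2). Subjects are taken as independent with a common rate.

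**Formula.** With X the number of subjects with a DLT, P(X ≥ 3) = 1 − P(0) − P(1) − P(2), where P(k) = C(n, k) p^k (1 − p)^(n − k).

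**Step 1: the plan's own figure (n = 12, p = 0.05).**

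- P(0) = 0.95^12 = 0.5404
- P(1) = 12 × 0.05 × 0.95^11 = 0.3413
- P(2) = 66 × 0.05² × 0.95^10 = 0.0988
- P(X ≥ 3) = 1 − 0.9804 = **0.0196**

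The plan prints 0.002. The ratio is 0.0196 / 0.002 = 9.8, that is, about 1 in 51 instead of 1 in 500.

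**Step 2: can 0.002 be reached another way?**

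| Variant | Probability |
|---|---|
| Exactly 3 of 12 at 5% | 0.0173 |
| Poisson, mean 0.6, 3 or more | 0.0231 |
| Normal approximation, without / with continuity correction | 0.0007 / 0.0059 |
| 3 or more of 10 at 5% | 0.0115 |
| 3 or more of 12 at 1% | 0.0002 |
| 3 or more of 20 at 1% | 0.0010 |
| **4 or more of 12 at 5%** | **0.0022** |

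Of these, only the tail for four or more rounds to 0.002: 0.01957 − 0.01733 = 0.00224. Using P(X > 3) in place of P(X ≥ 3) would produce it. So would typing 0.002 for 0.02, since 0.0196 rounds to 0.02. The documents do not show the calculation, so the cause is an inference.

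**Step 3: the rule as written (n = 20, p = 0.05).**

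- P(0) = 0.3585, P(1) = 0.3774, P(2) = 0.1887
- P(X ≥ 3) = **0.0755**, about 1 in 13

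A third DLT in subject 20 leaves no enrolment to halt. Requiring it within the first 19 subjects gives 0.0665, about 1 in 15.

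**Step 4: other true rates.** The rates of 10% and above are chosen for illustration; the documents name no unacceptable rate.

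| True DLT rate | 3 or more by subject 12 | 3 or more by subject 20 |
|---|---|---|
| 1% | 0.0002 | 0.0010 |
| 5% | 0.0196 | 0.0755 |
| 10% | 0.111 | 0.323 |
| 20% | 0.442 | 0.794 |
| 30% | 0.747 | 0.964 |

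**The case against.** The value 0.0196 is not open to dispute. The case on the other side is about how much follows from it.

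- **The 12-subject figure is labelled as such.** It can be read as a legitimate description of early stopping under a rule that continues to the end. This stands: the 20-subject value shows incomplete coverage and is not a second arithmetic error. The like-for-like comparison is 0.002 against 0.0196; setting 0.002 against 0.0755 compares different events. Even so, no section gives 12 subjects any role, and the rule over the full study is left undescribed.
- **No decision hangs on the number.** It sets no threshold, sample size or analysis. A trigger leads to a pause and review, the DSMC is told of every DLT and reviews them monthly (Sections 4.4 and 11.2), and its judgement would rest on case data. This also stands, and the effect on how a halt is read is a risk, not a certainty.
- **Subject protection is not weakened.** The rule triggers more often than stated, and at the expected rate of about 1% a halt stays rare (0.001 over 20 subjects). Section 5.2.1 reports no DLTs among 55 treated subjects. All this is true, but the plan chose 5% for its illustration, and at 5% its number is wrong.
- **Probabilities at higher rates are optional in an exploratory study.** This is fair. Their absence is a gap rather than an error, though they show what the rule can detect.

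**Conclusion.** The printed probability is wrong on its own inputs: 0.0196, not 0.002, a factor of 9.8. It also does not describe the rule in force, which covers all 20 subjects and at a 5% rate is triggered with probability 0.0755 (0.0665 if the third DLT must fall within the first 19). The significance level is irrelevant to the quantity stated.

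These values assume independent subjects, a common DLT rate and exactly 20 subjects at risk. The last may be slightly low. Section 4.2 says: "Any subject who does not receive the full panitumumab-IRDye800 dose will be considered withdrawn from the study and not count towards cohort accrual". If such subjects are replaced, more than 20 could be exposed, and if their DLTs count, the probability would be somewhat higher.

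The conclusion is limited to the stated operating characteristic. The stopping threshold, the eligibility criteria and the efficacy analysis are unaffected.

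**What to change.** In Section 2.4.2.2, replace the sentence containing 0.002 with the exact probability of three or more DLTs at 12 and at 20 subjects for true rates of 1%, 5%, 10%, 20% and 30%, using the table above. Delete the reference to a significance level. Either say why 12 subjects is of interest or report only the full-study figures, so that the stated probability, the rule in Sections 2.4.2.2 and 4.4, and the enrolment of 20 agree. State whether subjects who receive an incomplete dose count towards the three.

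The clinical rule needs no change for this purpose. The cost is one sentence or a small table, with a less favourable figure at 5%: 0.0196 by subject 12 and 0.0755 over the study.

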2.4.2.3. Pharmacokinetic intervals

Clearance of panitumumab occurs through the binding in the liver and through the reticuloendothelial system as occurs with endogenous immunoglobulin. Because the

pharmacokinetics of single dose panitumumab are well known and the pharmacokinetics of panitumumab and panitumumab-IRDye800 are nearly the same in non-human primate studies (see toxicology section), only limited pharmacokinetics will be performed. Blood levels of panitumumab-IRDye800 and free IRDye800 will be monitored on Day 0 before infusion and approximately 1hour after end of infusion), on Day 1 as available, on the day of surgery (Day 1 to 5 post-infusion), Day 1 to 3 post-surgery as available, Day of discharge, and Day 30 post-infusion of the study drug.

2.4.3. Workflow of the Clinical Trial

Below we provide a concise summary of the clinical trial workflow with regard to the different steps that are taken upon receiving of written informed consent from the study subject.

2.4.3.1. Panitumumab-IRDye800 Infusion

Subjects will be infused with 50 mg panitumumab-IRDye800 1 to 5 days prior to surgery. Further details on the infusion can be found in Section 4.1 and 4.2.

2.4.3.2. Preoperative Sentinel Node Mapping

Currently, SNB of squamous cell carcinoma of the head and neck is not performed at Stanford. It is however in the NCCN guidelines (7) where it is advocated as an alternative to neck dissection for loco-regional staging of the neck in subjects with either T1 or T2 stage and N0 status. For the subject work-up we will follow literature references on Lymphoseek in HNSCC (28), and the standard operating protocol the Division of Nuclear Medicine has in place for SNB of melanoma using Lymphoseek.

Current Procedural Terminology (CPT) codes are available for injection of the radiopharmaceutical Lymphoseek and (sentinel) lymph node mapping (38792 and 78195, respectively) in oral cavity cancer (ICD-10 codes C01-C06.9). The costs of the SNB procedure will therefore be billed to the subject's medical insurance.

Lymphoseek will be locally administrated the day before surgery. Peritumorally, 4 x 0.1 mL of Lymphoseek will be administrated. A total dose of maximally 2 mCi will be administered (28). Further details on Lymphoseek administration and radiation exposure are described in 4.1 and 4.3, respectively.

Preoperative SN mapping in subjects with HNSCC will be performed according to the protocol the Division of Nuclear Medicine has for Lymphoseek-based SN mapping in melanoma. Dynamic images will be acquired in anterior projection over the head and neck starting immediately after the injections have been completed. Lymphoscintigraphic imaging is performed at a 1 minute/frame for 30 minutes using a 128x128 matrix, followed by static spot views with/without a transmission source. Single photon emission computed tomography combined with computed tomography (SPECT/CT) imaging of the head and neck will follow the planar dynamic imaging. Acquisition parameters for a multi-detector system are 3-degree angular sampling, 128 x 128 matrix, 360-degree rotation and 20-30 sec per stop.

Following completion of image acquisition the Nuclear Medicine physician will review the images to determine the direction of the lymphatic flow and the potential accumulation in a sentinel LN. Using SPECT/CT images, he/she will determine the number and location of the SNs.

Rationale for SPECT/CT imaging: The value of SPECT/CT lies in the anatomical localization of the spot views seen on the dynamic planar images. Moreover, SPECT/CT may help to localize foci of abnormal Lymphoseek accumulation more accurately than planar imaging or SPECT alone.

Radiation risks associated with SPECT/CT imaging: It has been recommended that when SPECT/CT imaging is performed for anatomical correlation with the functional study, a low-dose CT scan is recommended. The radiation dose from low-dose CT scans will be approximately 0.6 mSv (70). This value is up to 80-85% lower than the radiation dose received when performing a diagnostic CT. As reported by Montes, *et al*, the main radiation risk for these low doses, in which stochastic effects predominate, is an increased probability of cancer induction – ranging 0.003 to 0.010% (71).

2.4.3.3. Intraoperative Imaging Protocol

On the day of surgery, 1 to 5 days post-infusion of panitumumab-IRDye800, intraoperative fluorescence imaging and gamma tracing will be performed.

Optical imaging devices to be used: Imaging with the optical imaging devices will be performed intraoperatively *in situ* and on the back table (see Appendix B for a list of the imaging devices). Additional ex vivo devices will also be used to image the specimens on the back table (see Appendix B for a list of the imaging devices).

All in vivo devices are FDA approved for measuring intraoperative blood flow after indocyanine green (ICG) injection. Because IRDye800 and ICG have overlapping excitation and emission spectra, each device can also be used for imaging subclinical disease based on our preclinical studies in head and neck cancer (see Appendix B for a list of the imaging devices).

Sentinel node biopsy (stage T1/2, cN0)

Step 1) *In situ* gamma tracing and fluorescence imaging of the sentinel nodes:

1. Prior to opening the skin, the surgeon will screen the neck for the presence of radioactive node(s) (ie, SNs) by sweeping the gamma probe over the intact neck. If any radioactive nodes are detected, the location of detected radioactive nodes will be marked on the skin using indelible ink and a still image of the marked will be collected for documentation.
2. After opening the skin, a photo of the neck will be taken for documentation. Hereafter the surgeon will perform fluorescence imaging of the neck to evaluate if there are any fluorescent nodes visible. Fluorescent nodes will be marked on the photo of the neck. Video and still images of the fluorescence imaging procedure will be collected.
3. Hereafter, as per standard of care, the surgeon will perform SNB using the gamma probe. For this, the surgeon will evaluate the neck with the gamma probe for the presence of radioactive nodes. Upon localizing of radioactive nodes, the count rate of the node will be determined. Then, just prior to the resection of the radioactive node, *in situ* fluorescence imaging will be performed to evaluate the fluorescence-based visibility of the node. For each radioactive node, the respective *in situ* location will be documented (level Ia, Ib, IIa, IIb, III, IV or V) as well as the radioactive status (count rate) and fluorescence status (yes/no). Hereafter the node will be harvested by the surgeon. This process will be repeated until no radioactive nodes are detected anymore *in situ*.

Step 2) Wound bed imaging:

As per standard of care SNB, upon completion of SNB, the neck will be screened once more with the gamma probe as such to determine the presence of any remaining radioactivity (ie, a radioactive signal detected > 10% of the background that correlates with any substrate (node). Areas in the wound bed determined radioactive-positive will be surgically re-evaluated, and, upon checking the fluorescence-status, removed, if deemed necessary by the surgeon. If any nodes are found, gamma tracing will be performed to determine the radioactive status.

Step 3) Pathological imaging:

The fluorescence and/or radioactive status of all excised nodes will be confirmed *ex vivo* on the back table using both a closed-field imaging device and an open-field device as well as the gamma probe, respectively. Hereafter all excised nodal specimens will be sent for (histo-)pathology. After the tissue has been processed and evaluated by the pathologist, imaging findings will be compared to gold-standard histological-assessment performed by the pathologist (including a hematoxylin and eosin (H&E) staining) to determine the correlation between fluorescence, radioactivity and the presence/absence of tumor tissue in the LN(s). Also findings will be compared to preoperative lymphoscintigraphy and SPECT/CT imaging (ie, correlation between preoperative imaging findings and intraoperative imaging findings).

Neck dissection only (T1-4, cN+)

After the neck has been opened by the surgeon, it will be inspected by the surgeon for the presence of suspicious nodes. Real-time fluorescence imaging of the LNs in the neck will then be performed at 4 time points:

Step 1) *In situ* imaging: After having opened the skin and exposure of the neck LNs, *in situ* fluorescence imaging will be performed to evaluate the fluorescence-based visibility of the LNs. For each fluorescent LN, the respective location will be documented (level Ia, Ib, IIa, IIb, III, IV or V) after which it will be harvested by the surgeon. This process will be repeated until no fluorescent LNs are seen *in situ*. Hereafter, the standard of care completion neck dissection will be performed.

Step 2) *Ex vivo* imaging: The neck dissection specimen will be evaluated for the presence of fluorescent LNs using both a closed-field imaging device and an open-field device. All additional fluorescent LNs will be identified, documented and collected separately; we acknowledge that the penetration depth of the fluorescence signal is limited and therefore deeper located LNs might not be detectable *in situ* (under step 1), but after having taken out the specimen and having “flipped” the specimen this might be possible.

Step 3) Wound bed imaging: This will be conducted for any remaining fluorescence (ie, any remaining fluorescent LNs). Areas in the wound bed determined fluorescence-positive will be surgically re-evaluated, and, if deemed necessary by the surgeon, removed.

Step 4) Pathological imaging: All excised nodal specimens will be imaged once more in the closed-field device to confirm that all fluorescent LNs have been removed from the neck dissection specimen. If not, the number and location of remainder fluorescent LNs will be documented after which they will be harvested; we will use the image taken under step 2 for reference as such to make sure that we did not create any confounding factor due to tissue

preparation to harvest nodes at step 2. Hereafter all excised nodal specimens will be sent for (histo-)pathology. After the tissue has been processed and evaluated by the pathologist, fluorescence imaging-based findings will be compared to gold-standard histological-assessment performed by the pathologist (including a hematoxylin and eosin (H&E) staining) to determine the correlation between fluorescence and the presence/absence of tumor tissue in the LN(s).

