10.2 Secondary Outcome Measure

The **secondary objective** of the study is to determine if panitumumab-IRDye800 can identify LNs with the same accuracy as Lymphoseek.

The **secondary endpoint** is: The number and location of Lymphoseek positive LNs that are also tumor-positive at (histo-)pathology. Comparison of the number and location of Lymphoseek positive LNs that are also tumor-positive at (histo-)pathology vs the number and location of panitumumab-IRDye800 positive LNs that are also tumor-positive at (histo-)pathology.

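### The count criterion for remaining radioactivity after sentinel node biopsy is met by background itself, so it cannot tell a radioactive node from a non-radioactive one

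*Combined protocol and SAP*

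**What the plan says.** All of this concerns Cohort 1, the sentinel node biopsy cohort (10 subjects, Section 2.4.2, Table 1).

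- **Step 1 (Section 2.4.3.3).** The surgeon searches the neck with the gamma probe: "Upon localizing of radioactive nodes, the count rate of the node will be determined". Each radioactive node is harvested, with its level, count rate and fluorescence status documented, and the search is repeated until no more are detected. No count rate is given above which a node is called radioactive.
- **Step 2, closing sweep.** The plan says that "upon completion of SNB, the neck will be screened once more with the gamma probe as such to determine the presence of any remaining radioactivity". Remaining radioactivity is then defined in brackets as "a radioactive signal detected > 10% of the background that correlates with any substrate (node". What follows from a positive reading is stated next: "Areas in the wound bed determined radioactive-positive will be surgically re-evaluated, and, upon checking the fluorescence-status, removed, if deemed necessary by the surgeon". After that: "If any nodes are found, gamma tracing will be performed to determine the radioactive status".
- **Step 3.** The radioactive status of all excised nodes is confirmed on the back table with the gamma probe, again without a cut-off.
- **Where the status is used.** The secondary endpoint in Section 10.2 begins: "The number and location of Lymphoseek positive LNs that are also tumor-positive at (histo-)pathology". Section 12.1.2 repeats this endpoint. It adds sensitivity and specificity of Lymphoseek against histology, and the odds of a false negative with panitumumab-IRDye800 relative to Lymphoseek-based biopsy.

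Sections 4.5 and 9.2.4 also mention gamma tracing, without a threshold. No section says how background is measured or asks for it to be recorded.

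**The concern.** A threshold for residual signal has to be able to return a negative answer at background level. This one is set at a tenth of background. Taken at its word, the count part returns positive for background and for a hot node alike.

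The defect matters statistically because radioactive status is the index-test result for Lymphoseek. Step 1 mainly collects nodes already judged radioactive. The closing sweep is one of the few points at which a non-radioactive node can enter the Cohort 1 data. If such a node is labelled by the written figure, one of two things happens:

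- A tumor-negative node moves from true negative to false positive, which lowers Lymphoseek specificity.
- A tumor-positive node moves from false negative to true positive, which raises Lymphoseek sensitivity and lowers its false-negative odds. The plan names false negatives as a particular concern.

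The same definition also triggers surgical re-evaluation of wound-bed areas.

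**Working it through.** **Inputs.** The trigger comes from Section 2.4.3.3, Step 2: signal > 0.10 × B, where B is the background count. The documents give no value for B and no counting time, so B is treated as unknown.

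**Literal rule, in expectation.**

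- Trigger = 0.10 × B.
- Background reading = 1.00 × B.
- Ratio = 1.00 × B / (0.10 × B) = 10.

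This holds for every B above zero and needs no assumption about count levels.

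**Literal rule, allowing for counting noise.** Assume Poisson counts and take B from 5 to 500 per reading (an assumed range). The probability that a reading passes is P(X > 0.10 × B).

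| B | Pure background passes | Source at 2 × B passes |
|---|---|---|
| 5 | 0.993 | 0.99995 |
| 10 | 0.9995 | 1.000 |
| 20 to 500 | 1.000 | 1.000 |

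For B = 5 the trigger is 0.5, so the two entries are 1 − exp(−5) = 0.99326 and 1 − exp(−10) = 0.99995. The specificity of the count criterion against background is 1 minus the middle column: 0.7% at most, and effectively zero from B = 20.

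**How much hangs on the missing reference quantity.** Suppose, purely for contrast, that the words meant 10% above background. The trigger would be 1.10 × B, which is 1.10 / 0.10 = 11 times the literal one. A reading at the background mean would then fail. A single noisy background reading would still pass with probability 0.38 (B = 5), 0.30 (B = 10), 0.15 (B = 100) or 0.013 (B = 500), and a source at 2 × B would pass with probability 0.93 to 1.00. This is an illustration and not a recommendation. It shows that the way background is measured matters as well as the percentage. Other reference counts would give other triggers, and the documents do not say which was meant.

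**Does anything else supply a cut-off?**

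- Step 1: a count rate is recorded, with no cut-off.
- Step 2, nodes found after the sweep: status is determined by gamma tracing, with no cut-off.
- Step 3: status is confirmed ex vivo, with no cut-off.
- Standard practice: Step 2 invokes standard of care, but Section 2.4.3.2 says that sentinel node biopsy for head and neck squamous cell carcinoma is not currently performed at the site. The work-up is to follow the literature and the site's melanoma protocol, so local practice does not clearly supply the meaning.

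**Reach.** The primary analysis (Section 12.1.1) sets fluorescence against histology, and the power calculation (Section 12.1.3) does not use a radioactivity threshold. Only the secondary analysis is exposed, through nodes found after Step 1 has been repeated to exhaustion. The plan does not say how many such nodes to expect, so no change in sensitivity or specificity can be computed.

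**The case against.** The strongest reply is that the count figure is only half of the sentence and does not act alone.

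1. **The signal must also correlate with a substrate (node).** A reader might infer from the arithmetic that every site in the wound bed would count as radioactive. The documents do not support that: an area with no node fails the second condition. This stands, and it limits the point to nodes. It does not repair the count part, because a non-radioactive node at background level meets both conditions. The text also speaks of areas being determined positive before it speaks of nodes being found.
2. **Removal is at the surgeon's discretion.** A reader might infer that the rule forces excision of normal tissue. It does not. A positive area is re-evaluated, and tissue is removed only after the fluorescence check and only if the surgeon judges it necessary.
3. **Late-found nodes get their own readings.** A reader might infer that Lymphoseek status of these nodes is meaningless. That goes too far. Step 2 measures them separately, Step 3 confirms all excised nodes, and the secondary endpoint does not cite the 10% figure. What remains is that neither later reading has a cut-off, so the written figure is the only number available to apply.
4. **It may be a slip of wording, with a usable definition in the site's melanoma protocol.** This is possible. That protocol is not part of the documents and cannot be checked. A surgeon is also unlikely to apply the words literally, but then each operator supplies a private threshold and the status is not defined by the plan.

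**Conclusion.** The point holds for the count criterion. As written, background exceeds the trigger tenfold, whatever the count level, and no other section corrects this or offers another cut-off.

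The effect on results is conditional. It arises only if the written threshold is used for the later node readings, and then only for non-radioactive late-found nodes in the 10 Cohort 1 subjects. Those nodes would be counted as Lymphoseek-positive in the secondary sensitivity, specificity and false-negative comparison. The size of that effect is not derivable from the documents. The Poisson figures rest on an assumed range of counts; the tenfold ratio does not.

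This should be corrected, but it does not threaten the primary endpoint or the stated power.

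**What to change.** 1. The sponsor must reconcile the Step 2 wording with the intended sentinel node biopsy procedure. The text should restate the reference quantity to which the percentage applies, and how background is measured, so that a background reading does not qualify. The choice of threshold belongs to the sponsor and the clinical team; none is proposed here.
2. State whether the corrected rule also governs the gamma readings of late-found nodes (Step 2) and of excised nodes (Step 3).
3. Record the background count rate and the count rate of every late-found node. Count rates of Step 1 nodes are already documented.
4. In Section 12.1.2, say that Lymphoseek status for the secondary endpoint is derived from the corrected rule and the recorded counts.

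The cost is one corrected sentence with a cross-reference, and a few extra recorded readings per Cohort 1 subject. Sample size and the primary analysis do not change.
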